The start of the study, i.e. the date at which follow up begins, will vary over centres and will be the date that GLP-1 RAs (exenatide in both formulations and liraglutide) were first available in the country or the date that the prescription registry has valid data from (whichever came last). From past experience from working on these databases (Boyle et al, 2013) we learnt that all three prescription registries were set up before the EU approval dates for exenatide. Therefore, the study period is defined as starting on 28 November 2006 (the EU approval dates are 28 November 2006 for exenatide and 02 July 2009 for liraglutide).

The end of the study is the date at which the follow up ceases for subjects who are still under observation (i.e. have not died or have not had pancreatitis/pancreatic cancer/thyroid cancer or known to be lost to follow up, perhaps because they have emigrated). [Note that patients with either one of the indicated adverse events will continue to be followed-up to monitor the diagnosis of another adverse event]. This date will be the date to which the hospital discharge registry and the cancer registry data are validated, 31 December 2013 for acute pancreatitis (in the Hospital Discharge Register) and through 31 December 2012 for pancreatic and thyroid cancer (in the National Cancer Registries). These initial dates may be extended in an additional follow-up of the study cohorts at the end of the 5 years; this remains to be re-viewed by the end of the 4th year of study.

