All patients who appear in the prescription registries of the countries with a record of prescription for anti-diabetes medication between the start date and end date for the centre are included in the analysis. Any patient without a record of prescription of any type of anti-diabetic medication will be excluded, as well as patients younger than 18 years at their start date. Patients with a cancer diagnosed prior to their start date (3) months after their date of first receiving anti-diabetic medication) will be excluded in the analysis as it is very unlikely that the cancer could be associated with the anti-diabetic treatment. We exclude the first 3 months from the beginning of anti-diabetes treatment because of the possibility that diabetes was caused by (or diagnosed following clinical workup for) cancer (reverse causality). As three months may be considered rather short and arbitrary length of the immortal time period to be excluded, a sensitivity analysis for exclusion of 6 months immortal time will be done. An eligible diabetes prescription is defined as only those occurring three months (or six months) or more before the censoring date (cancer, death and last date in registry). However, the three month (or six months) window will not apply for patients diagnosed with acute pancreatitis where, theoretically, this could be a rapid and acute response to an external stimulus such as therapy.

The starting date for an individual in the study is the date of first prescription of either exenatide or liraglutide for cohort 1 or the date of first prescription of other antidiabetics (e.g., oral anti-diabetics, insulins) for cohort 2 during the study period.

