A new user approach will be favoured in order to reduce prevalent user bias and confounding from covariates that could be associated with drug use (Ray, 2003). New users are defined as patients who initiated **either GLP-1 treatment or other antidiabetic drugs** at least 6 months after the start date of the study (this will include patients who are treatment naive in regards to any anti-diabetic medication although this group will be very few in numbers). The 6 months 'criterion' was defined in previous work on these databases (Boyle et al, 2013). Figure II.9.3.1 shows possible patient trajectories; incident users (with no history of anti-diabetic treatment) are patients 5, 6 and 7 on this diagram. As all prescription databases were set up relatively recently (i.e. 2004-2005), and we will have many patients in the cohort that developed diabetes long before that, the new user approach will deal with patients for whom we have complete data on the history of anti-diabetic medication.

The period of follow-up begins at that time or three months later until a specified event takes place, either (1) date of cancer/or acute pancreatitis diagnosis; (2) date of death (right censoring, only if death occurred before the last date of available data in registry); and, (3) last date of available data in cancer registry.

Figure II.9.3.1: possible patient trajectories

Acute pancreatitis cases will be identified from the hospital discharge registers. The diagnosis of acute pancreatitis is a clinical diagnosis that hinges on the presence of abdominal pain and elevation of two biomarkers, themselves not diagnostic. One potential issue to be faced is that abdominal pain can be an unwanted side effect of the use of GLP-1 medication and this could lead to diagnostic bias.

Cases of all thyroid cancers (especially medullary thyroid cancer) and pancreatic cancer will be identified from the national cancer registers. However, data on the cancer cases for a given year are typically considered incomplete until approximately one year after the year ends. Therefore, it will be possible to use the national cancer registries in these three countries to identify incident cancers occurring until the end of 2012, if the analysis of thyroid cancer is planned to be performed in early 2014.

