² An external blinded committee (Pancreatic Safety Assessment Committee or PSAC) has been appointed to review all pancreatic adverse events occurring in clinical trials of lixisenatide. The PSAC Charter has not been finalized, yet. However, the criteria for adjudication of acute pancreatitis will be adapted from those proposed by Banks, Freeman, and the Practice Parameters Committee of the American College of Gastroenterology (Am J. of Gastroenterology 2006;101:2379-2400) and Frossard et al. (Lancet 2008;371:143-52.).

Similarly to the Database Study, each national centre will be responsible for the data storage and data management of the individual-level data, following all national and European directives regarding the well being and rights of each study subject. Each centre has an excellent track record of successfully undertaking similar research respecting all moral and legal requirements.

Only de-identified data will be stored at IPRI, and this will be done in a secure manner: data will password protected, and stored on local machines.

III.9.7 Data Analysis

Descriptive analysis will be performed and total follow-up time for lixisenatide users will be calculated.

Figure II.9.7.3: General study overview

For acute pancreatitis, pancreatic cancer and thyroid cancer, the expected number of cases will be estimated annually after launch using the background rates obtained from the retrospective databases study.

If the observed number of cases for the events of interest, respectively, is significantly higher than the expected number of cases, further investigation may be warranted following discussion with the regulatory authorities.

An independent **Scientific Steering Committee** will be appointed to oversee the study and advise on treatment, methodological and biostatistical issues. This group will meet regularly throughout the duration of the study and incorporate a **Biostatistical Advisory Group**, to advise on all aspects of the design and data analysis.

The Scientific Steering Committee will comprise:

[name] University of Perugia Perugia, Italy

[name] University College London London, United Kingdom

[name] Robertson centre for Biostatistics University of Glasgow, Glasgow, United Kingdom

[name] Department of Biostatistics Yale University School of Public Health New Haven, United States of America

[name] McMaster University, Hamilton, Canada

[name] Mount Sinai Hospital New York, United States of America.

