Two separate data sets will be used for the analyses: one for all patients included in the prescription registry and a second analysis is intended, as far as possible, to isolate newly diagnosed patients. The second analysis data set will be referred to as patients with no history of insulin in the preceding 6 months (PNHIP6M) and are presumed new initiators of any type of insulin (example patients 7-11 on Figure 1).

0 t0

0 ti

0 t0

1 tg

0 ti

1 tg

1 t0

0 ti

1 tg

0 ti

1 tg

1 tg

1 ti

1 tg

1 ti

tc

tc

tg

tc

tg

tc

tc

tc

tc

tg

tc

ti

tc

ti

tc

Cancer

1

0

0

0

0

0

1

0

0

0

0

0

1

0

0

Ever Insulin Ever Glargine Start End

1

1

1

1

1

1

0

1

0

1

1

0

1

0

1

Figure 1: Illustration of different patient trajectories

In the trajectories **D** is date of diagnosis of Diabetes (which may not be known), **I** date of initiation of Non Glargine Insulin, **G** date of beginning Glargine, **C** Date of diagnosis of cancer, **Death** date of death and **EFU** date of end of follow up. Once a patient has entered the database of the treatment registry it will be assumed that the patient' therapy is known.

Table 3: Coding for survival model

(see also Appendix 4 for data
management example)

Ever/never analysis

Dose response analysis

	Glargine			
Patient	Dose Gp	start	end	Cancer
А	1	tg	tg+x	0
А	2	tg+x	tg+2x	0
А	3	tg+2x	tc	1
В	1	tg	tc	0
С	1	tg	tg+x 223	Pageo
С	2	tg+x	tc	0

Exclusion criteria

Any patient with no record of any prescription of any type of insulin will be excluded. Patients in the Prescription Registry with a cancer prior to their start date (or within 3 months of their start date) will not be included in the analysis as it is not feasible to associate the cancer with the insulin treatment.

An additional reason to exclude the first 3 months from beginning of insulin treatment is the possibility that diabetes was caused by (or diagnosed following clinical workout for) cancer (reverse causality).

Gestational diabetes patients (when we can identify them via a diabetes registry) will be excluded.

Person time at risk

All analyses will exclude the first 3 months from the numerator and denominator and there will be no built in 'immorality'

The 3 month exclusion will be applied to initiations of all new insulins (glargine/non glargine long acting/non long acting insulins). This will effectively be done by shifting all prescription dates by 3 months.

Contrasts

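### The early window is waived for patients who develop acute pancreatitis, not for the pancreatitis analysis; read literally, person-time then depends on the outcome

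*Protocol*

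**What the plan says.** Protocol II.9.3 (Dates) gives the reason for the window as reverse causality between cancer and diabetes: "We exclude the first 3 months from the beginning of anti-diabetes treatment because of the possibility that diabetes was caused by" cancer. It adds that "a sensitivity analysis for exclusion of 6 months immortal time will be done". An eligible prescription must precede the censoring date by at least the window, and the censoring dates listed are cancer, death and the last registry date. The exception follows: "the three month (or six months) window will not apply for patients diagnosed with acute pancreatitis", because pancreatitis could be a rapid reaction to therapy.

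On the start of follow-up, II.9.3 says that "The starting date for an individual in the study is the date of first prescription of either exenatide or liraglutide for cohort 1", and later that "The period of follow-up begins at that time or three months later until a specified event takes place". It does not say which start belongs to which patients or outcomes.

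Appendix III, the analysis plan of the glargine study that II.9.7 takes as its model, handles the window symmetrically: "All analyses will exclude the first 3 months from the numerator and denominator". For the Registry, III.9.7 says that "the expected number of cases will be estimated annually after launch using the background rates obtained from the retrospective databases study".

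**The concern.** A waiver attached to patients who are later diagnosed selects person-time by the outcome. Applied as written, a GLP-1 RA starter with pancreatitis in month 2 enters on day 0 and counts as an event, while an identical starter without pancreatitis enters at month 3. The prescription rule has the same flaw: a prescription two months before pancreatitis is eligible, but one two months before death or registry end is not. Appendix III avoids this by removing events and person-time together. II.9.3 takes over the eligibility rule without that safeguard and adds an outcome-based exception.

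Three things are at stake. Incidence rates are themselves part of the primary objectives (II.8). The hazard ratio can be distorted. The rates also feed the Registry, where pancreatitis exposure starts on the first day for everyone (III.9.3), so an inflated background rate would hide a lixisenatide signal. Under II.9.6 each country runs its own analysis and transfers only model coefficients, so different codings of this rule might not be visible centrally.

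**Working it through.** **Inputs.** Pancreatitis rate 65.57 per 100,000 person-years (Table II.9.5.1). GLP-1 RA follow-up averaging one year, 37,000 person-years at 5% exposure (II.9.5). Window L = 0.25 or 0.5 year (II.9.3). Registry person-years at 1% exposure 57,990.5 (Table III.9.5.1). Comparator follow-up is not given, so a range of 1 to 5 years is assumed.

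**The plan's own figures.** 750,000 × 5% × 1 year = 37,500 person-years, against 37,000 stated. Registry: 57,990.5 × 65.57/100,000 = 38.0 expected cases, as stated.

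**Symmetric handling.** Expected GLP-1 RA cases: 37,000 × 65.57/100,000 = 24.26. With no window for anyone the rate is 24.26/37,000 = 65.6 per 100,000. With the window removed from both sides it is (24.26 × 0.75)/(37,000 × 0.75) = 65.6. Neither is biased.

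**Literal rule, window counted from GLP-1 RA start.** All 24.26 cases stay, but almost everyone loses 0.25 year: 24.26/(37,000 × 0.75) = 24.26/27,750 = 87.4 per 100,000. In general the inflation is F/(F − L) for fixed follow-up F and exp(L/F) for exponential follow-up with mean F.

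| Mean follow-up F | L = 0.25, fixed | L = 0.25, exponential |
|---|---|---|
| 1 year | 1.333 (87.4) | 1.284 (84.2) |
| 2 years | 1.143 | 1.133 |
| 3 years | 1.091 | 1.087 |
| 5 years | 1.053 | 1.051 |

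With the six-month window at one year the factors are 2.00 (fixed) and 1.65 (exponential).

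**Ratio under a true null, literal rule, L = 0.25, both cohorts affected (fixed follow-up).**
- GLP-1 RA 1 year, comparator 1 year: 1.333/1.333 = 1.00. Simulated null Cox models gave 0.99–1.00.
- 1 year against 2, 3 and 5 years: 1.17, 1.22 and 1.27. Simulated at 3 years: 1.21–1.28.
- 2 years against 5 years: 1.143/1.053 = 1.09.

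**Other anchor.** If the window runs only from first-ever anti-diabetic treatment, GLP-1 RA time in previously treated patients is not lagged and only the comparator rate is inflated. The null ratio is then (F − 0.25)/F for comparator follow-up F: 0.75, 0.875, 0.917 and 0.95 at 1, 2, 3 and 5 years.

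**Registry.** 57,990.5 × 87.4/100,000 = 50.7 expected (48.8 with 84.2) instead of 38.0. A true observed/expected ratio of 1.5 would read as 1.5/1.333 = 1.13 (or 1.5/1.284 = 1.17).

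**The case against.** The strongest reply is that the literal reading was not intended. The window is justified only by cancer reverse causality, pancreatitis is absent from the censoring events in the eligibility sentence, and the reason for the waiver concerns the endpoint. II.9.3 has separate end dates for pancreatitis (2013) and cancer (2012) and says that "patients with either one of the indicated adverse events will continue to be followed-up to monitor the diagnosis of another adverse event". The Appendix I synopsis ends follow-up separately for each event and starts GLP-1 RA exposure on the first day of prescription. Follow-up starting at one of two times can therefore be read as one start per type of outcome. II.9.7 also defers full details to a later, approved analysis plan in the spirit of Appendix III. Much of this stands: an outcome-specific waiver is the likely intent, and a reader who infers one fixed clock per patient goes beyond the text. It does not remove the problem, because no sentence gives non-cases in the pancreatitis analysis the same waiver. This is a rule stated badly, not a detail left open.

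A reader might also infer that the plan will make a harmless drug look harmful by 30%. The documents do not support that. One year is the plan's conservative figure for the end of 2011, while pancreatitis follow-up runs to the end of 2013. Comparator follow-up is not stated. II.9.3 ties the window to the beginning of anti-diabetes treatment, not to the GLP-1 RA, and expects very few treatment-naive patients; under that anchor the bias reverses.

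Nor is it established that early pancreatic cancers presenting as pancreatitis would be kept in the cancer analysis. II.9.3 separately excludes cancers diagnosed before the three-month start date, with no exception for pancreatitis patients.

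**Conclusion.** The point holds as a badly worded rule with a conditional bias. Under the probable intent there is none. Under the literal reading, with the window counted from GLP-1 RA start, the GLP-1 RA pancreatitis rate is inflated by up to about 30% at one-year average follow-up, about 14% at two years and about 5% at five. The direction of any hazard ratio bias is not fixed by the text: about 1.0 with equal follow-up, about 1.2–1.3 under the null if comparators are followed 3–5 years against one (an assumption), and below 1 if the window runs only from first-ever treatment. For scale, the plan's minimum detectable risk for pancreatitis at 5% exposure is 1.80 (Table II.9.5.2). The Registry effect, up to about 51 expected cases instead of 38 at 1% exposure, rests on the same literal reading and the same one-year input.

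**What to change.** In II.9.3, replace the exception with an outcome-specific rule. In the acute pancreatitis analysis the window applies to no patient, case or non-case, and events, person-time and eligible prescriptions all count from the cohort entry prescription. In the pancreatic and thyroid cancer analyses the three-month (six-month) window applies to every patient, including those who have had pancreatitis, with events and person-time removed together as in Appendix III.

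In the follow-up paragraph of II.9.3, replace the two alternative starts with the start for each outcome, and say whether the cancer window runs from cohort entry or from first-ever anti-diabetic treatment.

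The cost is a few sentences of protocol wording and one start-date variable per outcome in the common analysis code. No new data are needed.

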Missing values for these variables will inevitably vary in proportion between variables and possibly between countries. The Biostatistical Advisory Group, a sub-committee of the Scientific Advisory Committee, will recommend a strategy for dealing with missing values taking into account the magnitude of the missing information for any one variable and any variation between countries (see below).

II.9.4 Data Sources

Denmark

The study will draw on health care databases covering the entire Danish population (approximately 5.3 million). The Danish National Health Service provides all inhabitants with free access to general practitioners and hospitals and refunds a variable proportion of prescription medication costs.

The Danish Civil Registration System keeps records on gender, date of birth, change of address, date of emigration and changes in vital status since 1968 (Frank, 2000). The records carry a 10-digit civil registration number (CRN), assigned to every Danish citizen and used in all Danish registers, enabling unambiguous record linkage between them. The CRN will enable the project to establish, for each individual under study, a complete hospital and prescription history since 1995.

The Register of Medicinal Products contains data from 1995 on almost all prescription drugs dispensed at all Danish pharmacies, including patients' CRN, the type of drug according to the anatomical therapeutic chemical classification system, and the date of dispensing the drug.

The Danish National Patient Registry (Andersen et al., 1999) collects data on all hospitalizations from Danish hospitals since 1977, including dates of admission and discharge, procedure(s) performed and up to 20 discharge diagnoses coded by physicians according to the International Classification of Diseases (8th revision [ICD-8] until the end of 1993 and 10th revision [ICD-10] thereafter). Inpatient admissions have always been collected; outpatient, day patient, and emergency room admissions have been collected since 1994.

Denmark has a high-quality National Cancer Registry which has existed since the early 1940s. Coverage and data quality have been shown to be complete from a variety of studies conducted using this resource and many influential epidemiological studies have been conducted and completed using it.

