Sweden	Prescription Database Start	1 July 2005	31 Dec 2009
	Glargine first used on		

End Date

For patients with an event (cancer) their last time on study is the date of cancer.

For patients who died without/with an event (cancer) their last time on study is the date of death or date the cancer registry closed (whichever is the earliest).

For patients with no event (cancer) and no entry in the Mortality Registry their last time on study is the date the cancer registry closed.

Start Date

The beginning of the study period will correspond to the first record of Glargine prescription in the country.

Glargine was first licensed in 2002 and there is merit in beginning the study in each centre at some time after this point as then the exposures to the different types of insulin will be relatively balanced over time. If a country has data prior to 2002 then this could be used to increase precision of the estimated effect of non glargine insulin by using a longer follow up time but would not have much impact on the estimated effect of Glargine use and the comparison of Glargine use with non Glargine use. Furthermore a bias may be introduced if there is a change to the detection of cancers – for example by screening effects which change over time.

For patients already in the Patient Prescription Registry at the beginning of the study period their start date will be the beginning of the study date.

For patients who are first recorded in the Patient Prescription Registry after the beginning of the study period their start date will be their date of first prescription.

Site	Code	-		
	ICD7	ICD8	ICD9	ICD10
All cancers (but non-melanoma skin cancers)	140-205 but 191	140-209 but 173	140-208 but 173	C00-C96 but C44
Breast *	170	174	174	C50
Colorectal **	153-154 **	153-154 **	153-154	C18-C21
Prostate	177	185	185	C61
Lung ***	162-163 ***	162	162	C33-C34
Pancreas	157	157	157	C25

Appendix 2: ICD codes Codification of cancer cases in cancer registries for Glagine study - based on ICD codes

* Only to be used for women ** Includes intestinal tract NOS => ICD7-8 no perfectly comparable to ICD 9-10

*** Includes trachea, bronchus and pleura => ICD7 no perfectly comparable to ICD 8-10

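### New-user status rests on a fixed 6-month calendar run-in rather than a per-patient look-back: it drops true first users of exenatide and can admit previously treated comparator patients

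*Protocol*

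**What the plan says.** Section II.9.3 favours a new-user approach to limit prevalent-user bias. New users are those who start GLP-1 treatment or another anti-diabetic drug "at least 6 months after the start date of the study". The stated gain is that "the new user approach will deal with patients for whom we have complete data on the history of anti-diabetic medication", and the section describes all the prescription databases as set up in 2004-2005.

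The start date is fixed in the same section: "the study period is defined as starting on 28 November 2006", because "the EU approval dates are 28 November 2006 for exenatide and 02 July 2009 for liraglutide". The section adds that "all three prescription registries were set up before the EU approval dates for exenatide". A comparator patient enters at the first prescription of another anti-diabetic "for cohort 2 during the study period".

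On the records held, section II.9.4 says of Denmark: "The Register of Medicinal Products contains data from 1995 on almost all prescription drugs dispensed at all Danish pharmacies". It dates the Norwegian registry from 2004. The table of dates in Appendix III (the glargine analysis plan) gives 1 January 2004 for Norway and, for Sweden, "Prescription Database Start 1 July 2005".

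**The concern.** A new-user design works by checking, for each patient, that the drug was not dispensed for a defined time before the index date. The rule here checks only where the index date falls in the calendar. That has two consequences.

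For GLP-1 RAs, study start is the first approval of the class, so there are no earlier users to screen out. The run-in can only discard genuine first users, and these have the longest possible follow-up in a study whose introduction already calls the follow-up very short for cancer.

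For other drugs, the run-in removes anyone dispensed during those six months but not someone treated earlier who paused through them. Such a patient would enter as new with the wrong treatment history. Section II.9.3 stratifies all analyses by treatment history and lists prior anti-diabetic use and duration of diabetes among the confounders. The database rates also supply the expected counts for the lixisenatide registry (III.9.7), so an error could carry over.

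**Working it through.** The plan gives no figure for either effect, so there is none to reproduce. The check is calendar arithmetic, with a month taken as 30.44 days.

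**Look-back available at study start (28 November 2006)**
- Sweden, from 1 July 2005: 515 days / 30.44 = 16.9 months.
- Norway, from 1 January 2004: 1,062 days / 30.44 = 34.9 months.
- Denmark, from 1995: 131 to 143 months, depending on whether data begin at the end or the start of that year.

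The shortest history is 16.9 months, so a common 16-month look-back is available in all three countries from the first day of the study.

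**Earliest new user under the rule**
- 28 November 2006 + 6 months = 28 May 2007, a run-in of 181 days.
- On that date the registers would support look-backs of 22.9 months (Sweden), 40.8 months (Norway) and 137 to 149 months (Denmark), against the 6 months used.

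**GLP-1 RA starters removed from the new-user set**

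Let T be the days from study start to end of follow-up and r = 181. Assume flat uptake and follow-up to study end. The share of starters lost is r/T; the share of person-time lost is 1 - ((T - r)/T)².
- Acute pancreatitis (to 31 December 2013), T = 2,590: 181/2,590 = 7.0% of starters; 1 - (2,409/2,590)² = 13.5% of person-time. Maximum follow-up falls from 7.09 to 6.60 years.
- Cancers (to 31 December 2012), T = 2,225: 181/2,225 = 8.1% of starters; 1 - (2,044/2,225)² = 15.6% of person-time. Maximum follow-up falls from 6.09 to 5.60 years.

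The documents give no uptake curve. With slow early uptake both shares tend to 0%. Only exenatide is affected, since liraglutide was approved in July 2009.

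**Comparator patients who could pass as new**
- Dispensed between 28 November 2006 and 27 May 2007: the first in-period prescription falls inside the run-in, so the patient is correctly screened out.
- Treated before 28 November 2006, nothing dispensed until 28 May 2007 or later: the first in-period prescription falls after the run-in, so the patient qualifies as worded, although the register holds the earlier record.

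The size of the second group depends on how often treated patients have a gap this long, which the documents do not give.

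**The precedent cited**

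Section II.9.3 takes the 6 months from earlier work on these databases. The glargine plan in Appendix III words its criterion per patient, as no insulin history in the preceding 6 months, and tests 8 and 12 months as sensitivity analyses. Its Norwegian and Swedish periods began when the prescription databases opened, so no earlier records existed there. Here they do. The 3-month versus 6-month sensitivity analysis in II.9.3 concerns the excluded time before cancer, not the washout.

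**The case against.** The strongest reply is that starting a drug can mean the first-ever record in the registry. Section II.9.3 describes incident users as having no history of anti-diabetic treatment and points to a trajectory figure that is not shown here. Section II.9.4 promises a full Danish prescription history since 1995. On that reading the comparator leak closes. This stands as a possible reading, but the entry date tied to the study period, and a part II synopsis that records medications prescribed in the study period, point the other way. The text has to settle it. The reading does nothing for the GLP-1 RA run-in.

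It can also be said that six months is defensible in itself: the dose rule in Appendix III does not count gaps above 181 days as exposure. That is fair. The complaint is about measuring six months on the calendar rather than per patient, and about leaving earlier records unused.

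Three stronger readings are tempting and not supported:
- **That early exenatide starters are lost to the study.** Section II.9.3 includes everyone with an anti-diabetic prescription in the period. The loss is confined to the new-user set, which is favoured but not stated to be the only analysis.
- **That prevalent patients swamp the new users.** Applying an assumed gap rate of 1% to 3% to the 750,000 patients in II.9.5 gives 7,500 to 22,500, or 14% to 41% of the 55,000 new cases a year in III.9.5. This sets a one-off stock against a single year. Over the 5.6-year new-user window for cancers, 55,000 × 5.6 = 308,000, and the share is 2.4% to 7.3%. Even that rests on a gap rate with no source in the documents and on a count that is not limited to drug-treated patients.
- **That comparators should be naive to all anti-diabetics.** The protocol says liraglutide is not approved as monotherapy in Europe and expects treatment-naive new users to be very few. Requiring naivety of the comparator cohort alone would set untreated patients against largely pre-treated GLP-1 RA starters and add imbalance.

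**Conclusion.** The point holds in two parts. For GLP-1 RAs the run-in screens out nobody and removes true first users of exenatide from the new-user set: 7-8% of starters and 14-16% of person-time under flat uptake and follow-up to study end, tending to nothing with slow early uptake. Section II.9.3 also lets the start vary by centre with local availability; on that reading the first six months after availability are dropped, so the defect remains.

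For other anti-diabetics, the rule as worded does not secure the complete history it claims and can admit previously treated patients with a long gap. The number affected cannot be computed from the documents. The 2004-2005 statement is also wrong for Denmark by the protocol's own section II.9.4. The definition should be changed; the documents do not show that the main cohort analysis is compromised.

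**What to change.** In II.9.3:
- Define a new user per patient as having no earlier dispensing of the initiated drug class in a common look-back of at least 16 months before the index date, using register records from before November 2006. Use the full look-back available in each country as a sensitivity analysis.
- Admit GLP-1 RA initiators from study start, without the 6-month run-in.
- Apply the same definition to both cohorts; do not require only the comparator cohort to be free of all earlier anti-diabetic drugs.
- Take the prior treatment history used for stratification from the same look-back.
- Correct the statement on the age of the databases for Denmark.

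The cost is revised wording, extraction of earlier anti-diabetic (ATC A10) records from the same registers, and a somewhat smaller comparator new-user set.
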